#### Reportable categories of Death

- Death attributable to a CTCAE term.
- Death Neonatal: A disorder characterized by cessation of life during the first 28 days of life.
- Death NOS: A cessation of life that cannot be attributed to a CTCAE term associated with Grade 5.
- Sudden death NOS: A sudden (defined as instant or within one hour of the onset of symptoms) or an unobserved cessation of life that cannot be attributed to a CTCAE term associated with Grade 5.
- Death due to progressive disease should be reported as **Grade 5 "Neoplasms benign, malignant and unspecified (including cysts and polyps) – Other (Progressive Disease)"** under the system organ class

(SOC) of the same name. Evidence that the death was a manifestation of underlying disease (e.g., radiological changes suggesting tumor growth or progression: clinical deterioration associated with a disease process) should be submitted.

#### 13.4.3 Secondary Malignancy

- A *secondary malignancy* is a cancer caused by treatment for a previous malignancy (e.g., treatment with investigational agent/intervention, radiation or chemotherapy). A secondary malignancy is not considered a metastasis of the initial neoplasm.
- All secondary malignancies that occur following treatment with an agent under an IND/IDE will be reported. Three options are available to describe the event:
  - Leukemia secondary to oncology chemotherapy (e.g., Acute Myelocytic Leukemia [AML])
  - Myelodysplastic syndrome (MDS)
  - Treatment-related secondary malignancy
- Any malignancy possibly related to cancer treatment (including AML/MDS) should also be reported via the routine reporting mechanisms outlined in each protocol.

#### 13.4.4 Second Malignancy

A second malignancy is one unrelated to the treatment of a prior malignancy (and is NOT a metastasis from the initial malignancy). Second malignancies require ONLY routine reporting unless otherwise specified.

#### 13.4.5 Pregnancy

##### **Procedures for Reporting Drug Exposure during Pregnancy and Birth Events**

[figure not shown]
If a woman becomes pregnant or suspects that she is pregnant while participating in this study, she must inform the investigator immediately and permanently discontinue study drug. The sponsor-investigator must fax a completed Pregnancy Form to the Millennium Department of Pharmacovigilance or designee. The pregnancy must be followed for the final pregnancy outcome.

If a female partner of a male patient becomes pregnant during the male patient's participation in this study, the sponsor-investigator must also immediately fax a completed Pregnancy Form to the Millennium Department of Pharmacovigilance or designee. Every effort should be made to follow the pregnancy for the final pregnancy outcome.

#### 13.4.6 Product Complaints

A product complaint is a verbal, written, or electronic expression that implies dissatisfaction regarding the identity, strength, purity, quality, or stability of a drug product. Individuals who identify a potential product complaint situation should immediately contact MedComm Solutions (see below) and report the

event. Whenever possible, the associated product should be maintained in accordance with the label instructions pending further guidance from a Millennium Quality representative.

Product complaints in and of themselves are not AEs. If a product complaint results in an SAE, an SAE form should be completed and sent to Millennium Pharmacovigilance (refer to Section 8.2).

A product complaint is a verbal, written, or electronic expression that implies dissatisfaction regarding the identity, strength, purity, quality, or stability of a drug product. Individuals who identify a potential product complaint situation should immediately contact MedComm Solutions (see below) and report the event. Whenever possible, the associated product should be maintained in accordance with the label instructions pending further guidance from a Millennium Quality representative.

A medication error is a preventable event that involves an identifiable patient and that leads to inappropriate medication use, which may result in patient harm. While overdoses and underdoses constitute medication errors, doses missed inadvertently by a patient do not. Individuals who identify a potential medication error situation should immediately contact MedComm Solutions (see below) and report the event.

### 13.5 Required Routine Reporting

Pretreatment symptoms/conditions to be graded at baseline and adverse events to be graded at each evaluation per CTCAE v4.0 grading **unless** otherwise stated in the table below:

CTCAE System Organ Class (SOC)	Adverse event/Symptoms	Baseline	Each evaluation
Blood and Lymphatic System Disorders	Anemia	X	X
Gastrointestinal Disorders	# of stools	X	
	Diarrhea		X
	Nausea	X	X
	Vomiting	X	X
	Mucositis Oral	X	X
General disorders and administration site conditions	Fatigue	X	X
	Injection site reaction		X
Investigations	Platelet Count Decreased	X	X
	Neutrophil Count Decreased	X	X
	White Blood Cell Decreased	X	X

CTCAE System Organ Class (SOC)	Adverse event/Symptoms	Baseline	Each evaluation
Metabolism and nutrition disorders	Anorexia	X	X
Renal and urinary disorders	Acute Kidney Injury	X	X
Skin and subcutaneous tissues	Rash acneiform	X	X
	Rash maculo-papular	X	X

**13.5.1 Submit via appropriate MCCC Case Report Forms (i.e., paper or electronic, as applicable) the following AEs experienced by a patient and not specified in Section 13.5:**

13.5.1.1 Grade 2 AEs deemed *possibly, probably, or definitely* related to the study treatment or procedure.

13.5.1.2 Grade 3 and 4 AEs regardless of attribution to the study treatment or procedure.

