### 2.2 Secondary Objectives

- 2.2.1 To evaluate the safety profile of each treatment regimen
- 2.2.2 To assess the impact on median progression-free survival with the addition of fulvestrant to alisertib
- 2.2.3 To obtain estimated tumor response rate and the median progression-free survival time during alisertib and fulvestrant treatment in the cohort of patients who progress during alisertib monotherapy, and crossover to receive the combination of alisertib and fulvestrant.

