### 3.3 Clinical data with fulvestrant

[figure not shown]
Fulvestrant is an FDA-approved agent for the treatment of post-menopausal ER+ metastatic breast cancer. It is a pure ER antagonist given by intramuscular injection in a 28-day cycle. It is exceptionally well-tolerated with the most frequent side effects being mild hot flashes and arthralgias. The CONFIRM trial is a published phase III randomized trial of fulvestrant (500 mg Day 1 and 15 of cycle 1 and 500 mg Day 1 of subsequent cycles) and fulvestrant (250 mg Day 1

[figure not shown]
each cycle) as first line treatment for advanced ER+ breast cancer. The trial population included patients who relapsed on adjuvant endocrine treatment or within one year of completing adjuvant endocrine therapy; for those with relapse >1year after completion of adjuvant therapy or de novo stage IV disease, progression on first line anti-estrogen therapy was required. Among 240 patients with measurable disease receiving the 500mg dose, the ORR was 13.8%. Fulvestrant can induce anti-tumor response in disease with prior hormonal treatment exposure; however, the ORR is less than desirable and in part reflects the scope of the problem of resistance to hormonal therapy.

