- Common ( $\geq 1\%$  and  $< 10\%$ ): lymphopenia, pancytopenia, dyspepsia, mucosal inflammation, URTI, UTI, pneumonia, oral candidiasis, sepsis (including fatal sepsis), cellulitis, oral herpes, sinusitis, nasopharyngitis, bronchitis, herpes zoster, influenza, conjunctivitis, esophagitis, skin infection, fungal skin infection, oral fungal infection, septic shock, increased AST, increased ALT, increased blood bilirubin, increased alkaline phosphatase, increased GGT, gait disturbance, confusional state, rash, pruritic rash, macular rash, maculo-papular rash, dermatitis acneiform, palmar-plantar erythrodysesthesia syndrome
- Uncommon ( $\geq 0.1\%$  and  $< 1\%$ ): sedation, dermatitis bullous

Reproductive toxicology studies have not been conducted with alisertib. Given the outcomes associated with Aurora A kinase inhibition and the effects of alisertib observed in reproductive tissues in repeat-dose toxicology studies, it is anticipated that alisertib could be a reproductive and developmental toxicant.

Because alisertib may cause anemia, neutropenia, leukopenia, lymphopenia, and thrombocytopenia, patients on alisertib may experience the anticipated sequelae of infection, hemorrhage, or bleeding.

Because of the effects of alisertib on the gastrointestinal mucosa, there is a potential risk of mucosal bleeding, GI bleeding, and the associated infections and sepsis.

Cases of cardiac abnormalities have been infrequently observed in patients receiving treatment with alisertib, including decreased left ventricular ejection fraction, tachycardia, and 1 case of QT prolongation. The causal relationship between cardiac dysfunction and alisertib has been confounded by patients' prior history of other cardiac abnormalities.

Alisertib is structurally related to the benzodiazepines and may cause somnolence, confusion, dizziness or gait disturbance associated with the onset of maximal plasma concentration (about 3 hrs post-dose). For this reason, patients should not drive, operate dangerous machinery, or perform any other task requiring full alertness and/or coordination if these effects are experienced while enrolled on study. Sedative effects have been managed by administration of divided doses and dose administration at bedtime, although dose reductions have sometimes been required.

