#### **Common known potential toxicities, >10%**

Endocrine & metabolic: Fertility; Hot flushes

Hepatic: Alkaline phosphatase increased, transaminases increased

Local: Injection site pain

Neuromuscular & skeletal: Joint disorders

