## 17. STATISTICAL CONSIDERATIONS AND METHODOLOGY

The aims of this clinical trial include assessing the impact of adding fulvestrant to alisertib in terms of clinical benefit (response rate and progression-free survival) and safety.

Among the patients who are assigned to alisertib monotherapy (Arm 1) who progress and choose to receive the combination of fulvestrant and alisertib, the primary aims are to examine response and the differences in time to progression with alisertib and that with fulvestrant and alisertib.

Initial treatment refers to alisertib alone for those randomized to Arm 1 and alisertib with fulvestrant for those randomized to Arm 2. Crossover treatment only applies to patients who progress during treatment with alisertib alone on Arm 1.

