### 17.1.2 Secondary Endpoints

- 17.1.2.1 Duration of response during initial treatment- time from randomization to disease progression among those patients whose disease meets the RECIST criteria for CR or PR on 2 consecutive evaluations approximately 8 weeks apart during initial treatment.
- 17.1.2.2 Clinical Benefit Rate (CBR) during initial treatment - the proportion of patients who have completed 6 cycles of treatment without disease progression (that is, their objective disease status is a CR, PR, or stable for 6 cycles or more) during initial treatment.
- 17.1.2.3 Progression-free survival (PFS) - time from randomization to disease progression or death due to any cause. If a patient has not had a disease evaluation within 3 months of death, the patient will be censored at the time of last disease evaluation for estimating the distribution of PFS time.
- 17.1.2.4 Safety Profile: The CTCAE version 4.0 will be used to grade and assign attribution to each adverse event reported during initial treatment and crossover treatment separately.

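### As Section 13.5 is written, hot flashes, arthralgia and somnolence are not solicited, so their any-grade rates in the safety profile are lower bounds

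*Combined protocol and SAP*

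**What the plan says.** Safety is a secondary objective (2.2.1): "To evaluate the safety profile of each treatment regimen". Section 17 also makes it part of the comparison, stating the aims as "assessing the impact of adding fulvestrant to alisertib in terms of clinical benefit (response rate and progression-free survival) and safety". The endpoint definition in 17.1.2.4 is: "The CTCAE version 4.0 will be used to grade and assign attribution to each adverse event reported during initial treatment and crossover treatment separately". The safety profile is thus built from whatever reaches the database as a reported event.

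Section 13.5 decides what reaches it. Its table names the terms graded at each evaluation at any grade, with no attribution filter. Section 13.5.1 then deals with "the following AEs experienced by a patient and not specified in Section 13.5". It asks for Grade 2 events only if judged at least possibly related, for "Grade 3 and 4 AEs regardless of attribution to the study treatment or procedure", and for deaths that meet its time or attribution conditions.

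On what to expect from the added drug, Section 3.3 describes fulvestrant as well tolerated, with "the most frequent side effects being mild hot flashes and arthralgias".

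**The concern.** The reporting rule and the expected toxicity do not match. Section 3.3 says that fulvestrant's most frequent effects are hot flashes and arthralgias and that they are mild. Mild events of unlisted terms are the ones that 13.5.1 does not require. Somnolence is in a similar position. Section 8.1.7 puts it above 10% with alisertib, 7.2 gives it its own dose rule from Grade 3, and 8.1.9.3 tells nurses to warn patients about it, yet it has no row in the table.

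At stake is how the adverse event tables can be read. Nausea or fatigue would be captured at every grade, while hot flashes would be captured only when related Grade 2 or worse. If both sit in one any-grade table, a nearly empty hot flash row could be taken as absence of the effect, although safety is part of what adding fulvestrant is meant to show. The sponsor uses low-grade data of this kind: the phase I summary in Section 3.6 reports cycle 1 Grade 1/2 events whatever their attribution. The Section 13.5 rules do not secure the same summary for these three terms.

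**Working it through.** The plan states no figure on this point, so the check is mainly a comparison of its sections.

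**Step 1: what is solicited.** The terms marked for each evaluation in 13.5 are anemia, diarrhea, nausea, vomiting, oral mucositis, fatigue, injection site reaction, decreased platelets, decreased neutrophils, decreased white cells, anorexia, acute kidney injury, acneiform rash and maculo-papular rash: 14 terms. Twelve also have a baseline grade; diarrhea uses stool count instead, and injection site reaction has none. Hot flashes, arthralgia and somnolence do not appear.

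**Step 2: what must be submitted, non-serious events.**

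| Worst grade | Listed term | Unlisted term |
|---|---|---|
| 1 | yes | no rule |
| 2, judged related | yes | yes |
| 2, judged unrelated | yes | no rule |
| 3-4 | yes | yes |

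Serious events of any term also reach the routine data, because 13.1 requires expedited reports to be entered there as well.

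**Step 3: rates the documents give.**

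- Hot flushes: above 10% with fulvestrant (8.2.7). This applies to Arm 2 and to crossover treatment, not to initial treatment in Arm 1.
- Joint disorders: above 10% with fulvestrant, but arthralgia by name is in the 1-10% list of the same section.
- Somnolence: above 10% with alisertib (8.1.7), so in both arms.

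No grade mix or attribution share is given for any of them. The listed rates may not carry over to this trial either. Section 4.1.5 requires prior fulvestrant for most patients, 4.3.1 excludes fulvestrant only within the last 21 days, and 8.2.5 gives a half-life of about 40 days (at 250 mg). Some symptoms may be present at entry, and 13.2 counts a prior condition as an event only if its severity or frequency has increased.

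**Step 4: illustration only.** Assume a true any-grade rate r, a share g of affected patients whose worst grade is 1, and every Grade 2 event judged related. Then:

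- rate that must be submitted = r × (1 − g)
- expected patients = 45 × r × (1 − g), with 45 per arm from 17.2
- chance that no case must be submitted in an arm = (1 − r(1 − g))^45

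| r | g | Rate submitted | Patients, true → submitted | Chance of none |
|---|---|---|---|---|
| 10% | 50% | 5% | 4.5 → 2.25 | 9.9% |
| 10% | 70% | 3% | 4.5 → 1.35 | 25.4% |
| 10% | 90% | 1% | 4.5 → 0.45 | 63.6% |
| 20% | 50% | 10% | 9.0 → 4.5 | 0.9% |
| 20% | 70% | 6% | 9.0 → 2.7 | 6.2% |
| 20% | 90% | 2% | 9.0 → 0.9 | 40.3% |

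With full capture at r = 10%, the chance of no case is 0.90^45 = 0.9%. Any Grade 2 event judged unrelated would lower the submitted counts further. The fraction lost is simply g, which is assumed, so the table shows how the rule works and does not estimate its effect.

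The 10% row is a fair starting point only for somnolence and, in patients on fulvestrant, hot flushes. For arthralgia at the 1% end of its listed range, full capture would give 45 × 0.01 = 0.45 patients and an empty row with probability 0.99^45 = 64%. An empty row is therefore not in itself evidence of lost events.

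**The case against.** A short solicited list, backed by related Grade 2 and all Grade 3-4 events, is an explicit collection rule that limits site workload. Neither 2.2.1 nor 17.1.2.4 promises any-grade incidence or a between-arm test of adverse events. Section 13.5.1 sets a minimum and does not stop sites from entering lower grades, and the forms packet mentioned in 13.5.2 cannot be seen. Other effects listed above 10% with alisertib, such as alopecia and abdominal pain, are also unsolicited. All of this stands. It makes the point minor and conditional, but it does not explain why the two effects that Section 3.3 singles out for the added drug have no row.

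Three stronger readings are tempting, and the documents do not support them.

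- A reader might infer that liver enzyme rises are under-counted in the same way, since 8.2.7 lists "Hepatic: Alkaline phosphatase increased, transaminases increased" for fulvestrant and 8.1.7 lists "increased AST, increased ALT, increased blood bilirubin, increased alkaline phosphatase, increased GGT" for alisertib. But 13.2 says that a laboratory value is an adverse event only if it leads to action or is judged a clinically significant change. Leaving out other values applies the plan's own definition. Values that matter clinically are still events under 13.2 and 13.3.3.
- A reader might infer that a stated percentage of events will be lost. That would need grade and attribution shares that the documents do not contain.
- A reader might infer a biased comparison between arms. Hot flashes and arthralgias come with fulvestrant, so missing mild cases would tend to shrink the contrast, and open-label judgments of relatedness could add a distortion for Grade 2. Neither can be sized. Somnolence is an alisertib effect and is subject to the same rule in both arms.

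**Conclusion.** The point holds in limited form. Under 13.5 and 13.5.1, non-serious Grade 1 events and Grade 2 events judged unrelated need not be recorded for hot flashes, arthralgia or somnolence. Their any-grade rates are then lower bounds, which matters most for the mild fulvestrant effects named in 3.3. This assumes that the forms carry no extra fields and that sites submit only what is required. The size of the loss is unknown.

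Not affected: the listed terms, related Grade 2 events, Grade 3 and above, serious events, the Grade 4 stopping rule in 17.5.2, and the primary endpoint. No sample size, power or alpha figure changes. Severity is minor.

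**What to change.** Add hot flashes, arthralgia and somnolence to the Section 13.5 table, marked at both Baseline and Each evaluation. The baseline grade matters because prior fulvestrant is usual in this population. The rows fit on the existing baseline adverse event form (14.1.2) and solicited adverse event form (14.1.3), with no new visit or test.

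The costs are more low-grade entries and different ascertainment before and after the change. The report must state the difference, preferably showing these terms separately for patients enrolled before and after. Symptom grades for past cycles cannot be recovered. The protocol is already at Amendment 8, so few patients may benefit.

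If enrollment is complete, leave the forms alone and state in the report that Grade 1-2 rates for these three terms are lower bounds. CTCAE grading of the liver tests already drawn each cycle is optional. It corrects no error and may need values retrieved from source records, since 14.1.2 and 14.1.3 list no laboratory form.

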13.5.1.3 Grade 5 AEs (Deaths)

13.5.1.3.1 Any death within 30 days of the patient's last study treatment or procedure regardless of attribution to the study treatment or procedure.

13.5.1.3.2 Any death more than 30 days after the patient's last study treatment or procedure that is felt to be at least possibly treatment related must also be submitted as a Grade 5 AE, with a CTCAE type and attribution assigned.

**13.5.2 Late Occurring Adverse Events**

Refer to the instructions in the Forms Packet (or electronic data entry screens, as applicable) regarding the submission of late occurring AEs following completion of the Active Monitoring Phase (i.e., compliance with Test Schedule in Section 11).

## 14. DATA AND SAFETY MONITORING

### 14.1 Data Management and Reporting

#### Submission Timetables

#### 14.1.1 Pre-Registration Material(s)

Case Report Form (CRF)	Active-Monitoring Phase (Compliance with Test Schedule Section 4.0)
Pre-Registration Screening Failure	Complete only if patient is NOT registered after she is pre-registered
Pathology materials	See Section 17.0 (for central review, eligibility, etc. confirmation prior to Registration)

#### 14.1.2 Initial Material(s)

CRF	Active-Monitoring Phase (Compliance with Test Schedule Section 11)
Pathology Materials (including local pathology report)	See Section 9 (for central review, eligibility, etc. confirmation prior to Registration/Randomization)
On-Study Form	≤2 weeks after registration
Adverse Events: Baseline	
Institutional Contact	
On-Study: Prior Disease History (Left Breast) as applicable	
On-Study: Prior Disease History (Right Breast) as applicable	
On-Study: Prior Neoadjuvant or Adjuvant Therapy	
On-Study: Prior Systemic Therapy for Metastatic Disease	
Metastatic Disease Status	
RECIST Measurement: Baseline	
Supporting Documentation: Baseline	
Specimen Submission: Tissue (see Section 9)	
Specimen Submission: Blood	
Patient Status: Baseline	
Off Treatment	Submit ≤2 weeks after registration if withdrawal/refusal occurs prior to beginning protocol therapy

**14.1.3 Test Schedule Material(s)**

CRF	At each evaluation during treatment	At end of treatment
Treatment (Intervention)	X 	X
Treatment (Intervention): Dose Modifications, Omission and Delays 	X	X
Adverse Event: Solicited	X	X
RECIST Measurements	X	X
RECIST Measurements: Cross-over Baseline  Arm 1 patients that cross-over only	X	
RECIST Measurements: Cross-over Arm 1 patients that cross-over only	X	X
Specimen Submission: Tissue	X (see Section 9)	
Specimen Submission: Blood	X (see Section 9)	
Supporting Documentation	X	X
Patient Status: Treatment (Intervention)	X	X
End of Initial Treatment  – Arm 1 patients that cross-over only		X
Off Treatment		X
Consent Withdrawal (choose appropriate withdrawal form): Specimen Only, All Follow-Up 	If applicable	
Lost to Follow-Up 	If applicable	
ADR/AER	At each occurrence (see Section 13)	

1. Complete at each evaluation during Active Treatment (see Section 11).
2. Complete only if applicable
3. At initial cross-over for Arm 1 patients only

